8.2 Statistical analysis

Statistical input has been sought from the University of Cambridge Statistics Clinic (PhD student [name] and his supervisor [name]) and will be supported by [name]. Inter- and intra-rater reliability testing will be performed for the MRE and axial MRI assessments using intra-class correlation coefficients (ICC). The proportion of CD cases with evidence of axSpA on MRE imaging who fulfil diagnostic criteria for axSpA will be expressed as a percentage. Further descriptive analyses will also be performed on study participants. Due to the possible preponderance of patients with axial pain willing to participate in the study and therefore selection bias, we will not be able to calculate the true prevalence of axSpA in CD patients.

As it is expected that the majority of data collected will be count data with an excess of zero-values, a zero-inflated Poisson (ZIP) regression model will be used to test for association between the presence of axSpA, MRE score, PROMs, clinical indices, site of CD and blood biomarkers. In addition, ZIP regression will be used to test for association between MRE scores and those of dedicated axial MRI scans. Zero-inflated binomial regression will be used as appropriate, where the mean approximates the variance. Two-tailed tests will be performed, and the alpha set at 0.05.

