1.6 Study schedule

The MRE scans of consenting patients will be reviewed for evidence of axSpA in the ProSpA-CD-Screen phase of the study. Case and control subjects meeting the inclusion criteria and giving informed consent as per section 5.2.2 will then be recruited in to the ProSpA-CD-Assess phase of the study. Consented subjects will complete the following patient reported outcome measures (PROM); Bath Ankylosing Spondylitis Disease Activity Index (BASDAI), Bath Ankylosing Spondylitis Functional Index (BASFI), a Visual Analogue Score for back pain (VASbp), Ankylosing Spondylitis Disease Activity Score (ASDAS) and Stanford Health Assessment Questionnaire Disability Index (HAQ-DI). Each subject will be examined in the SpA clinic using the Bath Ankylosing Spondylitis Metrology Index (BASMI), 68 tender joint count, 66 swollen joint count, the spondyloarthritis research consortium of Canada (SPARCC) enthesitis index, and for skin or nail psoriasis.

The following investigations will also be performed *as per* standard of care for the patients with axial skeleton abnormalities on their MRE (MRE+) and no known diagnosis of SpA, if clinically indicated and if not been performed in the preceding month; full blood count (FBC), renal function, liver function tests (LFTs), C-reactive protein level (CRP), erythrocyte sedimentation rate (ESR) and faecal calprotectin. *HLA-B27* testing will also be requested if not previously performed. These investigations will also be performed for the control subjects and the group of CD subjects with a known diagnosis of SpA who are MRE+ (if not performed in the preceding month and if *HLA-B27* not previously performed) but will be funded by the research grant, unless clinically indicated.

A dedicated axial MRI scan of the spine and sacroiliac joints will be performed in all case and control subjects if indicated by the clinical assessment as part of their standard NHS care. Subjects in whom a dedicated axial MRI scan is not clinically indicated, or those who have had one performed previously for a known diagnosis of SpA, will be consented to undertake the MRI scan for research purposes and the MRI scan will be funded by the research grant.

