Subjects meeting the inclusion criteria and giving informed consent as per section 5.2.2 will then be recruited in to the ProSpA-CD-Assess phase of the study. Consented subjects will complete the following PROMs; BASDAI, BASFI, VASbp, ASDAS and HAQ-DI [37-40]. Each subject will be examined in the SpA clinic using the BASMI, 68 tender joint count, 66 swollen joint count, the SPARCC enthesitis index, and for skin or nail psoriasis. The following investigations will also be performed as per standard of care for the patients with axial skeleton abnormalities on their MRE (MRE+) and no known diagnosis of SpA, if clinically indicated and if not been performed in the preceding month; FBC, renal function, LFTs, CRP, ESR and faecal calprotectin. *HLA-B27* testing will also be requested if not previously performed. These investigations will also be performed for the control subjects and the group of CD subjects with a known diagnosis of SpA who are MRE+ (if not performed in the preceding month and if *HLA-B27* not previously performed) but will be funded by the research grant unless clinically indicated.

A dedicated axial MRI scan of the spine and sacroiliac joints will be performed in all case and control subjects if indicated by the clinical assessment. Subjects in whom a dedicated axial MRI scan is not clinically indicated, or those who have had one performed previously for a known diagnosis of SpA, will be consented to undertake the MRI scan for research purposes and the MRI scan will be funded by the research grant.

All subjects (cases and controls) will be asked to further consent to provide research samples, including whole blood and stool, for storage and future analysis (serum for biomarker analysis, plasma for proteomic analysis, DNA for genotyping, and stool for microbiome analysis). Collection of these samples will be funded by the existing research grant, and analysis will be funded by research grants that are currently being applied for.

The control group will receive no further follow up unless clinically indicated. CD subjects in this group with a known history of SpA will be followed up as planned by their primary rheumatology team.

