5.2.2.1 Consent for retrospective review of the MRE scans (ProSpA-CD-Screen phase)

The gastroenterology team will write to all patients with CD and MRE scans since 2015 to ask for consent to review the images for evidence of axSpA. This correspondence will include a PIS and consent form with a stamped-addressed envelope for returns. The pack will also contain a BASDAI questionnaire with six simple questions relating to symptoms of axial inflammatory pain. These six questions, answered on a 1-10 VAS will pose low burden on the subject and be optional to complete, but will markedly help the research team gauge the impact of selection bias on the study given that there may be a preponderance of patients with axial pain willing to participate in the study.

5.2.2.2 Consent to enter the study as a case or control subject (ProSpA-CD-Assess phase)

Patients with lesions on MRE consistent with axSpA (and no known diagnosis of SpA) will be informed of this by the gastroenterology team (by telephone and letter) and be referred to [name] NHS SpA clinic for further clinical assessment. Once informed, they will also be invited by post to enter the research element of the study, with an invitation letter, accompanying PIS and reply slip (study interest form) with a stamped-addressed envelope to permit the patient to express if they do or do not wish to participate in the study.

CD subjects with a known diagnosis of SpA who are already under the care of a rheumatology team and have lesions on MRE consistent with axSpA will also be contacted by telephone and letter by the gastroenterology team. The subjects will then be sent a separate invitation letter, PIS and reply slip (study interest form) with a stamped-addressed envelope to permit the subject to express if they do or do not wish to participate further.

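### Section 8.2 assigns continuous PROMs, BASMI and CRP/ESR to zero-inflated Poisson regression; where one of them is the response, model-based p-values depend on its unit

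*Combined protocol and SAP*

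**What the plan says.** Section 8.2 opens its regression paragraph with the reason for the model: "As it is expected that the majority of data collected will be count data with an excess of zero-values". It continues that "a zero-inflated Poisson (ZIP) regression model will be used to test for association". The associations are listed in one phrase; the plan will "test for association between the presence of axSpA, MRE score, PROMs, clinical indices, site of CD and blood biomarkers". A second use of the same model, between MRE scores and dedicated axial MRI scores, follows.

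The only other model named is this: "Zero-inflated binomial regression will be used as appropriate, where the mean approximates the variance". Its trigger concerns the mean and variance, not whether the variable is a count. The paragraph ends: "Two-tailed tests will be performed, and the alpha set at 0.05". Nowhere does section 8.2 say which variable is the response, or give a model for continuous measures, a robust variance, a transformation or a unit.

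Section 4.1 lists the PROMs: "Consented subjects will complete the following PROMs; BASDAI, BASFI, VASbp, ASDAS and HAQ-DI". It adds BASMI, joint counts and the enthesitis index from the examination, and CRP and ESR among the blood tests. The only PROM scale that the documents describe is that of the BASDAI in the screening consent pack (section 5.2.2.1): "These six questions, answered on a 1-10 VAS will pose low burden on the subject". No unit is given for back-pain VAS, CRP or ESR.

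**The concern.** The premise fits some of the listed variables: tender and swollen joint counts, the enthesitis count and the SPARCC MRI sum scores. It does not fit rating scales, functional and metrology indices, or laboratory measurements. Yet PROMs, clinical indices and blood biomarkers are sent to the model by name.

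A Poisson model takes the variance to equal the mean. For a true count that can be checked, because the unit is one event. For a VAS or a concentration the mean and the variance change differently when the unit changes, so the assumed precision depends on how the value was recorded. The same back-pain data in cm or mm, or the same CRP in mg/L or mg/dL, could then give different conclusions. At stake are the comparisons of PROMs, BASMI and CRP/ESR by axSpA status, case/control group or CD site.

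**Working it through.** Section 8.2 ties no sample size or power figure to this model, so there is no figure of the plan to reproduce.

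**Inputs.** Group size 66 + 66, from section 8.1 (445 × 0.15 = 66.75). Two-sided alpha 0.05, from section 8.2. Assumed, because the documents give no values: back-pain VAS on 0-10 with mean 4 and SD 2.4.

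**Scaling.** For two groups the model-based Poisson standard error of the log ratio of means is SE = √(1/Σy₁ + 1/Σy₀). Replacing y by c·y leaves the log ratio unchanged and divides SE by √c, so z is multiplied by √c. For c = 10 the factor is 3.16: z = 1.00 (p = 0.317) becomes z = 3.16 (p = 0.0016). This is exact without zeros and close to it with zero inflation.

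**Expected error rate for the assumed VAS.**
- Model SE in cm: each group total is 66 × 4 = 264, so SE = √(2/264) = 0.087.
- Model SE in mm: each total is 2640, so SE = √(2/2640) = 0.0275.
- Actual SE in either unit: √(2 × (2.4/4)²/66) = 0.104.
- Ratio of actual to model SE: 1.20 in cm (√(5.76/4) = √1.44) and 3.79 in mm (√(576/40) = √14.4).
- Rejection with no true difference: 2 × [1 − Φ(1.96/1.20)] = 0.10 in cm; 2 × [1 − Φ(1.96/3.79)] = 0.61 in mm.

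**Simulation with no true difference, 66 per group, nominal 0.05.** All distributions are assumed.

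| Response and fit | Smaller-number unit | Larger-number unit |
|---|---|---|
| VAS mean 4, SD 2.4, plain Poisson (cm, mm) | 0.087 to 0.106 | 0.58 to 0.60 |
| VAS mean/SD 3/2, 4/2.4, 5/2.5, 3/2.5, plain Poisson | 0.08 to 0.18 | 0.58 to 0.67 |
| VAS, gamma with 10% zeros, full ZIP fit (cm, mm) | 0.10 | 0.64 |
| BASDAI 1-10, and the same values × 10, ZIP routine (no zeros, so plain Poisson) | 0.02 | 0.48 |
| CRP log-normal, median 4 mg/L (mg/dL, mg/L), ZIP routine (no zeros, so plain Poisson) | 0.07 | 0.57 |

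The first row covers three simulations with slightly different VAS shapes. The full ZIP and ZIP-routine rows have 400 runs each (Monte Carlo SE up to 0.025). As a control, data that really were zero-inflated Poisson counts gave 0.06 (SE 0.012), compatible with 0.05. Robust standard errors in the plain Poisson model gave 0.047 to 0.050 in cm and 0.050 to 0.057 in mm.

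**One illustrative data set.** With VAS as response the ZIP coefficient is 0.170 (SE 0.103, p = 0.100) in cm and 0.176 (SE 0.0315, p = 2 × 10⁻⁸) in mm. With CRP as response the coefficient is −0.129 in both units, but p is 0.088 in mg/L and 0.59 in mg/dL. Linear regression gives p = 0.233 for VAS and, on the log scale, p = 0.254 for CRP, in either unit.

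**Roles reversed.** With the MRE score as response and VAS or CRP as covariate, p does not move with the unit: 0.275 and 0.275 for VAS, 0.411 and 0.411 for CRP.

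**The case against.** The strongest reply is that section 8.2 never makes a PROM or a laboratory value the response. One coherent reading takes the MRE score as response, with axSpA, PROMs, clinical indices, site and biomarkers as covariates; the next sentence of the section again uses ZIP for MRE scores. On that reading the unit effect is absent, as the last check shows. This stands, and it makes the consequence conditional. It does not remove the point. Section 4.1 describes the Assess phase as ending in a comparison of cases and controls. Axial disease is binary and CD site categorical, so a ZIP comparison of a PROM by either one needs the PROM as response. Nothing in section 8.2 rules that out.

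Second, the mechanism is variance misspecification, so it overlaps with over-dispersion of true counts. That also stands: robust standard errors bring the rate back to about 5%. The difference is that, for these measures, the degree of misspecification depends on a unit that the plan does not fix.

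Third, the word majority in the premise allows for exceptions. But no model is supplied for them, and PROMs and blood biomarkers are named for ZIP.

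Three stronger readings are tempting and are not supported:
- A reader might infer that these scales contain no zeros at all. The 1-10 scale is documented only for the screening-pack BASDAI; the other PROMs may have zeros.
- A reader might extend the point to full blood count, renal and liver values. Section 8.2 says blood biomarkers, and section 6.4 lists stored serum biomarkers apart from the routine tests, so whether those values are included is unclear. CRP and ESR are the more natural examples, though section 6.4 lists them with the routine tests too. Faecal calprotectin is a stool test.
- A reader might infer that every PROM test would be too liberal. BASDAI on its 1-10 scale rejected only 2% of the time.

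**Conclusion.** The point holds in conditional form. Section 8.2 prescribes a zero-inflated count model for measures that are not counts and offers no continuous alternative. When such a measure is the response with model-based standard errors, z scales with the square root of the unit. For a back-pain VAS under the assumed values, a nominal 5% test rejects about 10% of the time in cm and about 60% in mm. The exact rates depend on assumed distributions; the square-root scaling does not.

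It would be wrong to conclude that the main results are at risk. Sensitivity, specificity and AUC (section 4.3.3) do not use this model, objectives 2 and 3 are proportions, and no sample size rests on it. This is a should-fix matter for the secondary association analyses.

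**What to change.** In section 8.2:
- State the response and the explanatory variables for each association.
- Limit zero-inflated count models to joint counts, the enthesitis count and the SPARCC MRI sum scores.
- When a PROM, BASMI, CRP or ESR is the response, use linear regression with robust standard errors (log scale for CRP and ESR), or a rank or proportional-odds model, adjusted for the matching factors age and sex.
- Use axSpA status as the explanatory variable only in those PROM, BASMI and laboratory models. Objective 5 asks whether CD site predicts axSpA, so there axSpA remains the response.

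The cost is SAP wording and standard software; no new data or visits are needed.

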4.3 ProSpA-CD-Assess phase

4.3.1 Assessment of patients with lesions on MRE consistent with axSpA (cases)

Patients with lesions on MRE consistent with axSpA (and no known diagnosis of SpA) will be informed by telephone and letter by the gastroenterology team and referred to [name] NHS rheumatology SpA clinic. They will also be sent separately an invitation letter, participant information sheet (PIS) and reply slip (study interest form with a stamped-addressed envelope for returns) for the ProSpA-CD-Assess phase of the study by the gastroenterology team. CD subjects with a known diagnosis of SpA who are already under review by rheumatology and who have lesions on MRE consistent with axSpA will also be considered as cases and will be sent an invitation letter, PIS and study interest form. However, they will instead be invited to attend the rheumatology SpA research clinic to be assessed for axSpA (with the control group) as this will be considered to be outside of their routine NHS care.

In the NHS SpA clinic, the patients will be assessed by a single rheumatologist ([name], in a supernumerary capacity with salary funded by the research grant) for clinical evidence of axSpA *as per* standard of care using the 2009 ASAS criteria for axSpA, modified New York criteria for AS and CASPAR criteria for PsA (see Appendices 5, 6 & 7). The assessment will include a clinical history, examination (including BASMI, 68 tender joint count, 66 swollen joint count, the SPARCC enthesitis index and for skin or nail psoriasis), PROMs (BASDAI, BASFI, VASbp, ASDAS and HAQ-DI), blood samples (FBC, renal function, LFTs, CRP and ESR unless performed in the preceding month, and HLA-B27 unless previously performed) and stool samples (the monitoring of IBD luminal activity with faecal calprotectin is well established [41, 42]; stool samples will therefore also be collected to measure faecal calprotectin concentrations unless performed in the preceding month). During the consultation, the ProSpA-CD-Assess phase of the study will also be discussed further and patients will be provided with the opportunity to ask any questions they may have regarding the study. If they agree to participate in the study and meet the inclusion criteria, then written informed consent will be taken. The blood and stool tests will be performed as per standard of care if clinically indicated or for research and funded by the research grant if not clinically indicated.

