4.3.2 Assessment of subjects with no lesions on MRE consistent with axSpA (controls)

Subjects (including those with a known diagnosis of SpA) who have consented to having their MRE scans reviewed, but who do not have lesions consistent with axSpA, will be informed in writing of this by the gastroenterology team. They will also be advised that they may be invited to enter the study as a control subject if they are randomly selected through matching (age and sex) to the enrolled 'MRE+ cases' (1:1 ratio). Matched potential control subjects will then be sent an invitation letter, PIS and reply slip (study interest form with a stamped-addressed envelope for returns) by the gastroenterology team to attend the rheumatology SpA research clinic to be assessed by [name] for clinical evidence of axSpA. CD subjects with a known diagnosis of SpA who are already under review by rheumatology and who have lesions on MRE consistent with axSpA will also be invited to attend this clinic for review outside of their routine NHS care but will be considered as cases. Informed consent for study participation in the SpA research clinic will be performed at the start of the consultation. The same clinical assessments, blood and stool samples and dedicated axial MRI scan of the spine and sacroiliac joints will be performed in this control group and in the group of CD subjects with a known diagnosis of SpA who are MRE+ as in the other cases, but will be funded by the research grant unless clinically indicated.

Control subjects in whom there is no evidence of axSpA (by ASAS, modified New York or CASPAR classification criteria) will be informed by letter, which will also be copied to the subjects GP and gastroenterology consultant. Control subjects who do have evidence of axSpA will be informed by letter (also copied to GP and gastroenterology consultant) and asked to return to [name] NHS rheumatology SpA clinic for ongoing care. CD subjects who already have a diagnosis of SpA (both in the control group and cases group) and are already under review by a rheumatology team will be informed by letter of the research clinic outcome and will be followed up as planned by their primary rheumatology team. We will also send a copy of the clinic letter to their GP, gastroenterology consultant and named rheumatology consultant to inform them of the clinic findings and to notify them of any outstanding tests/ management plans that may need to be considered at the next clinic review.

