Appendix 1: Study Flow Chart

Appendix 2: Schedule of Procedures

Procedure	Timeline / visits			
	Months 0-6	Months 7-12 (screening/ baseline)	Months 13-18 (follow-up)	Months 19-24
Patient consent for MRE image review and recruitment	●			
MRE training and scoring	●			
Systematic literature review	●			
Demographics		●	●	
Medical history		●	●	
Clinical examination		●	●	
PROMs		●	●	
Blood tests as per standard of care or research		●	●	
'Research' tests (blood and stool samples)		●		
Faecal calprotectin as per standard of care or research		●	●	
Dedicated axial MRI as per standard of care or research, with two expert scorers		●		
Statistical analysis			●	●
Write-up of MD thesis and associated papers				●

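### Section 8.2 tests CRP and ESR against axSpA with no measure of current bowel inflammation, although faecal calprotectin is planned for consenting Assess-phase subjects and enters no named analysis

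*Combined protocol and SAP*

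**What the plan says.** Section 8.2 (Statistical analysis) states that zero-inflated Poisson regression will be used to "test for association between the presence of axSpA, MRE score, PROMs, clinical indices, site of CD and blood biomarkers", and that "Two-tailed tests will be performed, and the alpha set at 0.05". It gives no adjustment set for any of these models. The only other text in 8.2 that could take in further variables is "Further descriptive analyses will also be performed on study participants".

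Section 4.3.1 explains why stool is tested: "the monitoring of IBD luminal activity with faecal calprotectin is well established". It goes on: "stool samples will therefore also be collected to measure faecal calprotectin concentrations unless performed in the preceding month". Of the blood work and the stool samples alike it says that they "will be performed as per standard of care if clinically indicated or for research and funded by the research grant if not clinically indicated". For controls, and for MRE-positive subjects with known SpA, section 4.3.2 says: "The same clinical assessments, blood and stool samples and dedicated axial MRI scan of the spine and sacroiliac joints will be performed". Section 6.5 provides the calprotectin kit to subjects who consent to the research element. CRP and ESR are among the routine bloods (sections 4.3.1 and 6.4).

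Every subject has Crohn's disease (5.1.1). Controls are matched to MRE-positive cases on age and sex only (4.1, 4.3.2, 5.2.1.2).

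**The concern.** CRP and ESR are general inflammatory markers. In a cohort made up wholly of Crohn's patients they can rise because of the bowel as well as the sacroiliac joints and spine. The plan measures bowel activity and says why, but leaves it out of the models in which it would be most useful. Calprotectin is a stool test, so the phrase on blood biomarkers in 8.2 does not cover it. Site of CD is in the list, but it records where the disease is, not how active it is now. Matching does not help: it ignores bowel activity, and it is by MRE result rather than by axSpA status.

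If subjects with axSpA have more active bowel disease than the others, a CRP or ESR association can appear with no axial contribution. If they have less active bowel disease, a real axial contribution can be masked. The plan as written gives the reader no way to tell these apart.

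**Working it through.** The plan states no figure on this point, so there is none to reproduce. The check has two parts.

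**1. Text.** Calprotectin appears as a collected test in sections 1.6, 4.1, 4.3.1, 6.5, 7.1 and Appendix 2. It does not appear in section 8. Sections 4.3.1, 4.3.2 and 6.5 together plan it for consenting Assess-phase subjects, case or control, unless done in the preceding month.

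**2. Possible size.** Inputs from the documents: 66 + 66 = 132 subjects (8.1) and a two-sided alpha of 0.05 (8.2). Inputs that are assumed because the documents give none:
- proportion with axSpA, p = 0.40;
- correlation of gut activity with CRP on a normal scale, r = 0.4 or 0.6;
- correlation of gut activity with the latent axSpA liability, ρ = 0.1 to 0.3;
- no direct link between CRP and axSpA.

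A linear model stands in for the zero-inflated model because CRP and ESR are continuous.

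Difference in gut activity between the axSpA groups, in SD units: d = ρ·φ(t)/[p(1−p)], with t = 0.2533 and φ(t) = 0.3863. So d = ρ × 0.3863/0.24 = 1.610ρ.

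Spurious CRP difference: r·d.

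Standard error: √(1/52.8 + 1/79.2) = 0.1777.

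Rejection rate: Φ(rd/0.1777 − 1.96) + Φ(−rd/0.1777 − 1.96).

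Worst cell (r = 0.6, ρ = 0.3): d = 0.483, rd = 0.290, rd/SE = 1.631, and the rate is Φ(−0.329) + Φ(−3.591) = 0.371.

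| r | ρ | rd | Formula | Simulation, 3,000 runs |
|---|---|---|---|---|
| 0.4 | 0.1 | 0.064 | 6.5% | 6% |
| 0.4 | 0.2 | 0.129 | 11.2% | 12% |
| 0.4 | 0.3 | 0.193 | 19.3% | 18% |
| 0.6 | 0.1 | 0.097 | 8.5% | 9% |
| 0.6 | 0.2 | 0.193 | 19.3% | 19% |
| 0.6 | 0.3 | 0.290 | 37.1% | 37% |

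With ρ = 0, rd = 0 and the rate is 5.0% whatever the value of r.

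*Group split.* The axSpA split is not in the documents. With d set directly between 0.2 and 0.5 and r between 0.2 and 0.6, the formula gives 5.6% to 40.7% for 66 v 66 and 5.5% to 36.9% for 44 v 88. The result depends little on the split.

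*After adjustment.* If gut activity itself could be used as the covariate, the simulated rate returns to 4% to 6%. Calprotectin is an imperfect marker. Suppose it correlates q = 0.7 with gut activity (assumed). The remaining spurious difference is about rd(1−q²) = 0.51rd, and the residual SD is √(1−r²q²).
- Worst cell: 0.51 × 0.290 = 0.148; SE = 0.1777 × 0.908 = 0.161; ratio 0.917; rate about 15%.
- Mildest cell: 0.51 × 0.0644 = 0.033; SE = 0.1777 × 0.960 = 0.171; ratio 0.193; rate about 5.4%.

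Simulation with the same q gave 6% to 14%. The correction is real but partial.

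**The case against.** The strongest counter-argument is that 8.2 promises association, not an axial-specific effect. The unadjusted CRP association in Crohn's patients is a legitimate quantity. Section 2.1 says that SpA and IBD share cytokine pathways, so calprotectin may carry part of the same inflammatory process, and conditioning on it may remove real signal. This stands as a reason not to replace the unadjusted estimate. It does not stand against showing both. It is also true that 8.2 names no covariates for any model, so this is one instance of a general gap; it differs in that the variable is specific and already planned for collection.

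Several stronger readings are tempting, and the documents do not support them:

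- *That the main result is biased.* Sensitivity, specificity and AUC compare the MRE reading with the reference standard and involve no blood-marker regression.
- *That a stated purpose of CRP and ESR goes unmet.* None of the five objectives in 3.2 is a blood-biomarker association. Objective 4 concerns extra-articular features, and CRP and ESR are presented largely as standard-of-care tests.
- *That calprotectin exists for every subject.* It is planned for consenting Assess-phase subjects only. Sections 1.6 and 4.1 make it conditional on clinical indication for MRE-positive subjects without known SpA, although 4.3.1 funds it for research otherwise. Stool return may be incomplete.
- *That it can enter no analysis at all.* The unspecified descriptive analyses might tabulate it, but that would not adjust the tests.
- *That every blood marker needs the covariate.* HLA-B27 and genotype are not caused by current bowel inflammation. The stored-sample work is deferred to a later date and its funding is still being sought (4.3.1).
- *That MRE-score models need it too.* The MRE may date from 2015, while recruitment and data collection run from December 2018 to February 2020 (1.7). Stool at assessment does not measure bowel activity at a scan that may be years older.

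**Conclusion.** The omission is real and limited to secondary association tests. As written, 8.2 cannot separate bowel from axial inflammation in a CRP or ESR association with axSpA, and the one direct measure of bowel activity that the study plans to collect is left unused in any named analysis.

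The size is conditional. It needs luminal activity to be related both to the blood marker and to axSpA status, and the documents quantify neither. A reader should not take 37% as the study's error rate: that figure needs both assumed correlations at the top of their range, and the low end is about 6%, barely above nominal. The documents do not show that confounding is present, only that the plan could not detect it. This is worth correcting before analysis because it is cheap and because choosing the covariate in advance avoids a data-driven choice later.

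**What to change.** Add to section 8.2:

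- Models of CRP and ESR against axSpA status, and against the dedicated axial MRI score obtained at assessment, are reported both unadjusted and adjusted for log faecal calprotectin. The same holds for any later inflammatory serum or plasma marker. It does not hold for HLA-B27 or genotype.
- Calprotectin is reported by axSpA status.
- The number of subjects in each model is stated. Section 8.3 deals only with questionnaires, so it should also say how a missing stool result is handled.
- The interval between blood and stool samples is reported, since either may come from the preceding month and stool may be returned at the MRI visit (6.7).
- Calprotectin is not used as a confounder correction in MRE-score models, because of the time gap.
- The adjusted estimate is read with caution: it may under-correct because the marker is imperfect, and over-correct if gut and axial inflammation share pathways.

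Cost: a few sentences and no new data collection. The downside is that subjects with no stool result drop out of the adjusted model, which is why the unadjusted estimate and both sample sizes should stand beside it.
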